**Clinical Trials Protocol for “Reward Processes and Rehearsal in Exposure Therapy”
(NCT06132425)**

Last updated and approved on September 26th, 2023
(IRB#23-000236)

Study Description:

The purpose of this study is to 1) examine the importance of self-reported relief following exposure and 2) test whether positive-focused rehearsal following exposure can improve treatment outcomes for participants who endorse fear of public speaking. Exposure therapy is an extinction-based behavioral technique, often employed in the context of cognitive behavioral therapy. It involves strategically exposing an individual to a feared stimulus in an effort to generate new non-fear associations with that stimulus. Relief refers to the positive, rewarding emotions associated with the absence of an expected aversive outcome following exposure to a feared stimulus. In the current study, participants will engage in a series of short public speaking exposures that take place over two sessions. After every two exposures, participants will be asked to complete either a positive or neutral rehearsal exercise, consisting of recalling either positive or neutral aspects of the speech exposures. At multiple points throughout the study, participants will complete ratings of reward sensitivity, positive affect, relief, and expectancy of the aversive outcome. We will test whether 1) participants with higher reward sensitivity and positive affect will report more relief after each exposure, and 2) participants who report experiencing more relief after each exposure will learn more quickly that the feared stimulus does not predict an aversive outcome (i.e., learning rate). We will also test whether participants who engage in the positive rehearsal exercise will show 1) greater reduction in public speaking anxiety symptoms at the end of the study, 2) greater improvements in reward sensitivity and positive affect, and 3) a faster learning rate and changes in relief over the course of the study. The sample will be volunteer UCLA undergraduates who endorse fear and avoidance of public speaking, measured by two Likert scale screening questions. They will come in at two time points: Visit 1 (first set of exposures) and Visit 2 (second set of exposures), and will complete a few short surveys one week after Visit 2.

Background & Significance:

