Participants will complete rehearsal exercises after every two exposures to ensure there is sufficient content for rehearsal. Learning rate (change in expectancy of an aversive outcome across exposure trials) and relief rate (change in relief ratings across exposure trials) will be calculated based on self-reported expectancy and relief ratings provided after each exposure. We hypothesize that regardless of rehearsal group assignment, participants with reduced baseline reward sensitivity and positive affect will exhibit a slower relief rate relative to individuals with elevated baseline reward sensitivity and positive affect, and that lower positive affect will be associated with lower subsequent relief ratings relative to higher positive affect. We hypothesize that regardless of group assignment, higher relief ratings after the first exposure will be associated with a faster learning rate on subsequent exposure trials. Finally, we hypothesize that the positive rehearsal group will lead to significantly greater reductions in symptoms of social phobia and greater increases in reward sensitivity and positive affect at the end of the study, as well as faster learning and relief rates relative to the neutral rehearsal group.

Research Design & Methods:

Visits will either be conducted over HIPAA-compliant video conferencing platform Zoom or in person.

OVERVIEW

The experiment will consist of two study visits. Visit 1 will include informed consent and questionnaires. Participants will then complete a series of short 1-minute public speaking

exposures. After every two exposures, participants will complete a rehearsal task where the participant is asked to use a positive or neutral approach to remember and recount the exposures they have just completed (for a total of approximately 60-90 minutes). Visit 2 will occur approximately 1 week after Visit 1 and will consist of another series of short 1-minute public speaking exposures, followed by the same rehearsal task after every two exposures. Participants will then be asked to complete another series of questionnaires (for a total of approximately 60-90 minutes) For the rehearsal task in Visits 1 and 2, participant will be randomized to practice rehearsing a) focusing on positive emotional aspects of the exposures, or b) focusing on neutral, factual aspects of the exposures. One week after Visit 2, participants will be asked to complete a brief set of questionnaires (approximately 5-10 minutes).

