Prospective participants will be recruited through the UCLA Psychology Department Subject Pool (i.e., SONA). Prior to signing up for the study, prospective participants recruited through SONA will complete two public speaking anxiety screening questions as part of SONA's prescreening process to determine eligibility for participation. The questions are "How anxious would you feel giving a formal speech before a live audience?" and "How likely would you be to avoid taking a class that required an oral presentation?" Both questions are rated from 0 to 8, with zero indicating no anxiety/never avoid and 8 indicating extreme anxiety/always avoid. Eligible participants must report a score of 6 or higher on the first question and a score of 5 or higher on the second question. Participants will be assigned course credit after participating in the study. Participants will sign up for the study only if they are able to make both visits of the experiment. If the participant does not attend both visits, course credit will still be given for the amount of time the participant spent doing the experiment (i.e., 1 credit for 1 hour).

VISIT 1

On Visit 1, participants will first provide informed consent after the nature of the study has been fully explained and the participant has had time to ask questions. After obtaining informed consent participants will complete a demographics and eligibility questionnaire, which will be reviewed by the researcher upon completion. Ineligible participants (i.e., participants with scores below a 6 on public speaking anxiety and below a 5 on public speaking avoidance, who do not speak English, or are below 18 years of age) will be informed that they do not meet criteria and the research session will be terminated at this time. Participants participating for credit who are found to be ineligible will still receive .5 credits for their time.

Participants will then complete the remaining study questionnaires, the Liebowitz Social Anxiety Scale (LSAS, Leibowitz, 1987), Personal Report of Public Speaking Anxiety (PRPSA, McCroskey, 1970), 8-item version (excluding the suicide item) of the Patient Health Questionnaire-9 (PHQ-9, Kroenke et al., 2001), Positive Valence System Scale (PVSS, Khazanov et al., 2020), Behavioral Activation Scale (BAS, Carver & White, 1994), and a visual analog scale that assesses current positive and negative emotions on a scale from 1-9 (1=neutral/no emotion, 9=extreme emotion; adapted from Lang, 1980).

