After every two exposure trials, participants will then complete a rehearsal exercise (either positive or neutral rehearsal depending on their group assignment). Before the rehearsal exercise, participants will complete the visual analog scale to assess current mood. Participants will then be presented with instructions to complete a verbal rehearsal of the two exposures they just completed, followed by a written rehearsal of the two exposures they just completed. After the rehearsal exercise, participants will again rate their current mood using the visual analog scale, US expectancy ratings ("If you were to complete the same exact speech again, how likely is it that the feared outcome would occur?" where 0 = certain the feared outcome will not occur, 50 = completely uncertain, and 100 = certain the feared outcome will occur; and "Did the feared outcome occur?" where 0 = no, and 1 = yes), and relief ratings ("How relieved are you that the feared outcome did not occur?" where 0 = not at all, 50 = moderately, and 100 = very).

This entire process will be repeated four times, resulting in a total of 8 exposure practices and 4 rehearsal exercises. Participants will then complete a brief set of questionnaires including the LSAS, PRPSA, PVSS, and BAS. The visit is expected to take approximately 60-90 minutes to complete.

FOLLOW-UP

After completion of Visit 2, approximately one week later participants will be sent a short list of questionnaires to be completed independently. Surveys include the public anxiety screening questions, PRPSA, PVSS, and BAS and are expected to take 5-10 minutes to complete.

After completion of the follow-up surveys, participants will be compensated for their time one credit per hour of study participation. All participants will additionally be provided with a referral list at the end of the study.

Statistics & Data Analysis:

Sample size. The sample size will be 74 participants (37 per group). An a priori analysis using G*Power (Faul et al., 2007) indicated that a sample size of 74 would be sufficient to detect a significant effect based on a similar previous study ($d=.30$; Craske et al., 2019) with a power of .80 and an alpha of .05.

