Reward sensitivity and positive affect predicting relief. Linear mixed models will be utilized to assess whether baseline reward sensitivity, measured by the Positive Valence System Scale (PVSS, Khazanov et al., 2020) and the Behavioral Activation Scale (BAS, Carver & White, 1994), and positive affect, measured by a visual analog scale, predict relief rate over the course of exposures. Relief rate will be calculated using a computational model derived from the Rescorla-Wagner model (Rescorla & Wagner, 1972) to capture change in self-reported relief ratings over time. A linear mixed model will also be utilized to assess whether positive affect before an exposure trial predicts subsequent relief on the same trial.

Relief predicting learning rate. A linear mixed model will be utilized to assess whether relief after the first exposure trial predicts learning rate for subsequent exposure trials. Learning rate will be calculated using a computational model derived from the Rescorla-Wagner model (Rescorla & Wagner, 1972) to capture change in self-reported US expectancy ratings over time.

Comparison of positive and neutral rehearsal exercises. A repeated measures between-subjects ANOVA will be utilized to test whether participants in the positive rehearsal intervention show greater reductions in anxiety symptoms (public speaking anxiety screening questions; LSAS, Liebowitz, 1987; PRPSA, McCroskey, 1970) or greater increases in positive affect or reward sensitivity relative to participants in the neutral rehearsal intervention. We will use paired samples t-tests to test whether participants in the positive rehearsal intervention show a faster learning rate or relief rate relative to participants in the neutral rehearsal intervention.

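### Only one of the three anxiety outcomes, the PRPSA, is listed at both post-treatment points, and the end of the study is not defined, so whichever point is meant one named outcome has no value there

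*Combined protocol and SAP*

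**What the plan says.** **Outcomes and analysis.** In the combined protocol and SAP, Statistics & Data Analysis (Comparison of positive and neutral rehearsal exercises), a repeated measures ANOVA is to test whether positive rehearsal gives "greater reductions in anxiety symptoms (public speaking anxiety screening questions; LSAS, Liebowitz, 1987; PRPSA, McCroskey, 1970"). No occasions are named for any of the three.

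**Target time.** Specific Aims predicts "greater reductions in symptoms of social phobia and greater increases in reward sensitivity and positive affect at the end of the study". The Study Description words the anxiety hypothesis as "greater reduction in public speaking anxiety symptoms at the end of the study". Neither section says whether that time is the close of Visit 2 or the one-week follow-up.

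**Schedule, from Research Design & Methods.**
- Overview: prospective participants "complete two public speaking anxiety screening questions as part of SONA's prescreening process to determine eligibility for participation". The same cut-offs are checked again in the Visit 1 eligibility questionnaire.
- Visit 1: "Participants will then complete the remaining study questionnaires, the Liebowitz Social Anxiety Scale (LSAS" and others, among them the PRPSA.
- Visit 2, after the last exposure and rehearsal: "Participants will then complete a brief set of questionnaires including the LSAS, PRPSA, PVSS, and BAS".
- Follow-up, about one week later and completed independently: "Surveys include the public anxiety screening questions, PRPSA, PVSS, and BAS and are expected to take 5-10 minutes to complete".

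**The concern.** The three anxiety outcomes are grouped in one analysis description and tied to one target time, but they do not share a schedule. The LSAS stops at Visit 2. The screening questions skip Visit 2 and return at follow-up. Three things are at stake.

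- **A value at the hypothesised time.** As the time is undefined, it could be fixed after the data are seen, and either choice leaves out one named outcome.
- **Persistence.** The only post-treatment LSAS is taken in the same session as the last eight exposures and four rehearsals. The Background section cites prevention of return of fear as part of the rationale, yet the plan could not show whether an LSAS difference lasts a week. Nor could it show whether a screening-question difference at follow-up was already present when treatment ended.
- **Interpretation.** The LSAS and the screening questions share no post-treatment occasion. If they disagree, the scale and the timing are largely entangled.

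An occasion that was not measured cannot be recovered by analysis later.

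**Working it through.** **Step 1. Occasions listed for each outcome** (Research Design & Methods):

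| Outcome | Baseline | End of Visit 2 | One-week follow-up | Post-treatment readings |
|---|---|---|---|---|
| PRPSA | Visit 1 | yes | yes | 2 |
| LSAS | Visit 1 | yes | not listed | 1 |
| Screening questions | prescreen and Visit 1 eligibility check | not listed | yes | 1 |

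**Step 2. The two meanings of the end of the study.**
- Close of Visit 2: the PRPSA and LSAS have a value; the screening questions do not.
- One-week follow-up: the PRPSA and screening questions have a value; the LSAS does not.

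The Follow-up section mentions a referral list given at the end of the study, just after it describes the surveys. That leans towards follow-up but is not a definition.

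**Step 3. The plan's own sample size, as context.** The plan gives N = 74 for d = .30, power .80 and alpha .05. It states neither the number of occasions m nor the correlation ρ between them, so both are assumptions here. For a group-by-time interaction with two groups, f = d/2 = 0.15, and sphericity assumed:

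λ = f² × N × m / (1 − ρ), with df1 = m − 1 and df2 = (N − 2)(m − 1).

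- m = 3, ρ = .5: λ = 0.0225 × 74 × 3 / 0.5 = 9.99, df 2 and 144, power .806. The smallest N with power of at least .80 is 74, which matches the plan.
- m = 2, ρ = .5: λ = 0.0225 × 74 × 2 / 0.5 = 6.66, df 1 and 72, power .72. The N needed is 90.
- m = 2 with ρ from .3 to .7: the N needed runs from 126 to 56, and power at 74 from .58 to .91.

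The match at m = 3 is not unique: m = 2 with ρ = .6 gives 72, and m = 4 with ρ = .4 gives 76.

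**Step 4. What a second post-treatment reading could add.** Assume unit variance, equal correlation r between all occasions, and the same arm effect at both post-treatment points.

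- Change score, one post reading: variance 1 + 1 − 2r = 2(1 − r).
- Change score, mean of two post readings: (1 + r)/2 + 1 − 2r = 1.5(1 − r).
- Ratio: 1.5/2 = .75, a 25% cut at any r.
- Baseline-adjusted: 1 − r² with one reading, (1 + r)/2 − r² with two averaged.

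| r | one reading | mean of two | ratio | cut |
|---|---|---|---|---|
| .4 | .84 | .54 | .64 | 36% |
| .5 | .75 | .50 | .67 | 33% |
| .6 | .64 | .44 | .69 | 31% |
| .7 | .51 | .36 | .71 | 29% |
| .8 | .36 | .26 | .72 | 28% |

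These cuts apply only if the two readings are averaged. If a single occasion is named as the endpoint, that contrast does not gain them.

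**The case against.** The case for leaving the plan as it is has real weight.

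- **No analysis fails.** The ANOVA can be read as one model per outcome. A baseline and one post-treatment reading are enough to test group by time for the LSAS and for the screening questions. This stands.
- **A named measure exists under either meaning.** The Study Description words the hypothesis as public speaking anxiety. The PRPSA, a public speaking scale, is taken at both points, and two of the three measures are taken at each. This stands.
- **Timing is not wholly lost.** The PRPSA shows whether the arm difference in public speaking anxiety changes between Visit 2 and follow-up. It can be set beside the LSAS at Visit 2 and beside the screening questions at follow-up. This is partial information: it does not give the time course of the other two scales.
- **The plan promises no one-week LSAS result**, and a short follow-up battery may be a deliberate limit on burden. That is fair, but the plan does not give this reason.
- **The lists are not expressly exhaustive**, since both are introduced by a form of the word include. This is a minor point: the named scales differ between the two lists, and nothing says that the unlisted ones are given.

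A reader might infer from the Specific Aims wording, "the positive rehearsal group will lead to significantly greater reductions in symptoms of social phobia", that social phobia has no reading at the end of the study, because the LSAS is the one named scale for social anxiety in general. The documents do not support that. The LSAS is taken after the last exposure and rehearsal, and it lacks the required reading only if the phrase means follow-up, which is not stated.

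**Conclusion.** The schedule gap is real and can be checked directly. The PRPSA has two post-treatment readings, the LSAS has one (Visit 2) and the screening questions have one (follow-up). With the end of the study undefined, one of the three named anxiety outcomes lacks a value at the target time under either meaning, and one-week persistence of an LSAS difference cannot be tested. This rests on reading the two questionnaire lists as complete.

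It is a worthwhile and inexpensive improvement. The planned comparisons can still be run. Two further inferences should not be drawn:

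- **That 74 is the wrong sample size.** The match to a three-occasion design depends on an assumed ρ of .5, and a two-occasion design with ρ = .6 also reaches .80 power at 74 (.81).
- **That the extra readings would automatically sharpen the result.** The 25% cut for change scores, and 28–36% with baseline adjustment for assumed r = .8 to .4, needs both post-treatment readings averaged, equal correlations and a stable arm effect. If the effect fades between Visit 2 and follow-up, the last assumption fails.

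**What to change.** 1. Add the two screening questions to the battery at the end of Visit 2.
2. Add the LSAS to the follow-up survey. All three anxiety outcomes then share the PRPSA schedule: baseline, end of Visit 2, follow-up.
3. Define the end of the study in Specific Aims, and state in Statistics & Data Analysis whether the confirmatory anxiety contrast uses Visit 2, follow-up or the average of both. Name the occasions that enter each ANOVA.

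The cost is a small protocol amendment, two more items at Visit 2 and one more self-report scale in the follow-up survey. The documents give no completion time for the LSAS; a few extra minutes is an assumption, and the stated 5–10 minutes for the follow-up survey would need updating. Recruitment, sample size and the intervention are unchanged.

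If the schedule cannot be changed, step 3 is still needed. The report should then say that the LSAS result applies to the end of Visit 2 only and the screening-question result to follow-up only.

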Visit 2 will occur approximately one week after Visit 1. Participants will first complete ratings on the visual analog scale to assess current mood. Participants will then undergo 8 exposure trials for durations of 1 minute each. Prior to the first exposure, participants will be asked to record their feared negative outcome (e.g., social rejection). During each exposure trial, they will first complete self-reported current fear/anxiety ratings ("How fearful and anxious are you right now about giving this speech?" where 0 = not at all, 50 = moderately, and 100 = very) and US expectancy ratings ("How likely is it that the feared outcome will occur?" where 0 = certain the feared outcome will not occur, 50 = completely uncertain, and 100 = certain the feared outcome will occur). Participants will then have 10 seconds to look at a speech topic followed by one minute of giving this speech to an audience of two confederates. Immediately after the exposure, participants will complete self-reported current fear/anxiety ratings ("How fearful and anxious are you right now after giving this speech?" where 0 = not at all, 50 = moderately, and 100 = very), US expectancy ratings ("If you were to complete the same exact speech again, how likely is it that the feared outcome would occur?" where 0 = certain the feared outcome will not occur, 50 = completely uncertain, and 100 = certain the feared outcome will occur; and "Did the feared outcome occur?" where 0 = no, and 1 = yes), and relief ratings ("How relieved are you that the feared outcome did not occur?" where 0 = not at all, 50 = moderately, and 100 = very). Participants will then be given another speech topic and will follow the same procedure.

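### Positive affect is to be compared at the end of the study, but its last rating comes straight after the final rehearsal and none is listed for the one-week follow-up

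*Combined protocol and SAP*

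**What the plan says.** All references are to the combined protocol and SAP.

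- **Hypothesis.** Specific Aims expects the positive rehearsal group to show "greater increases in reward sensitivity and positive affect at the end of the study".
- **Measure.** Statistics & Data Analysis names "positive affect, measured by a visual analog scale". The Visit 1 section describes it as "a visual analog scale that assesses current positive and negative emotions on a scale from 1-9", so it is a rating of the moment.
- **VAS schedule.** It is given at the Visit 1 baseline and before and after each rehearsal at both visits. At the start of Visit 2, "Participants will first complete ratings on the visual analog scale to assess current mood". On the post-rehearsal rating, the Visit 2 section says: "After the rehearsal exercise, participants will again rate their current mood using the visual analog scale".
- **Closing questionnaires at Visit 2.** "Participants will then complete a brief set of questionnaires including the LSAS, PRPSA, PVSS, and BAS". The VAS is not named.
- **Follow-up.** The Overview says "One week after Visit 2, participants will be asked to complete a brief set of questionnaires". The Follow-up section gives the content: "Surveys include the public anxiety screening questions, PRPSA, PVSS, and BAS". The VAS is not named here either.
- **Analysis.** Statistics & Data Analysis tests the group difference in positive affect with a repeated measures ANOVA. It does not say which VAS occasions enter.

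**The concern.** The arms differ in what participants are asked to recall after the speeches: positive emotional aspects in one, neutral factual aspects in the other. A rating of current emotion made right after that recall is where a passing difference between arms is most to be expected. If that rating serves as the end-of-study value, a significant result cannot tell a brief mood response to the task from a rise in positive affect that outlives it.

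Positive affect is one of the named efficacy outcomes. The Background also makes it part of the route by which positive rehearsal should strengthen learning. Public speaking anxiety (PRPSA and the screening questions) and reward sensitivity (PVSS, BAS) each have a reading a week after the last rehearsal. Positive affect does not, so the same question cannot be answered for it.

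**Working it through.** **1. The VAS occasions, counted from the Visit 1 and Visit 2 sections**

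| Occasion | Readings | What comes just before |
|---|---|---|
| Visit 1 baseline | 1 | Questionnaires |
| Visit 1, before and after each of 4 rehearsals | 8 | Two speeches (before); a rehearsal (after) |
| Start of Visit 2 | 1 | About a week without study tasks |
| Visit 2, before and after each of 4 rehearsals | 8 | Two speeches (before); a rehearsal (after) |
| Closing Visit 2 questionnaires | 0 listed | n/a |
| One-week follow-up | 0 listed | n/a |

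Total: 1 + 8 + 1 + 8 = 18.

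**2. What each kind of reading can show**

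- The start-of-Visit-2 reading is not tied to a rehearsal just done. It can show carry-over over about a week, but only from the first 4 of 8 rehearsals.
- The reading before the last rehearsal comes after 7 of 8 rehearsals, but directly after two feared speeches.
- The reading after the last rehearsal is the only one that follows all 8, and the arm-specific task has only just ended.

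No scheduled reading therefore both follows the whole intervention and stands clear of a rehearsal just completed.

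**3. The plan's own figure**

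The stated sample size is 74 (37 per group) for d = .30, power .80, alpha .05. It can be reproduced as the group-by-time interaction of a repeated measures ANOVA under assumptions that the plan does not state: f = d/2 = .15, 2 groups, m = 3 occasions, correlation .5, sphericity.

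λ = f² × N × m / (1 − ρ) = .0225 × 74 × 3 / .5 = 9.99, with 2 and 144 degrees of freedom; power = .806.

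Other assumptions also come close, such as 2 occasions with correlation .6, which gives N = 72. The figure has no bearing on when the VAS is taken. It shows only that three occasions per outcome is one plausible reading of the planned ANOVA.

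**4. How readily a transient lift would reach significance**

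Inputs: n = 37 per arm and alpha .05 from the plan. Two-sided testing and lifts of .3, .5 and .8 SD are assumptions, because the plan gives no VAS effect.

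Noncentrality = d × √(n/2) = d × √18.5, with 72 degrees of freedom.

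| Assumed lift (SD) | Noncentrality | Power |
|---|---|---|
| .3 | 1.29 | .247 |
| .5 | 2.15 | .564 |
| .8 | 3.44 | .924 |

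With baseline and last reading as two ANOVA occasions, the group-by-time test equals a t-test on change, with effect d / √(2(1 − ρ)). At ρ = .5 this gives the same values. At ρ = .3 they are .19, .43 and .82; at ρ = .7 they are .38, .78 and .99.

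These figures say how often a lift of a given size would be detected. They do not say that such a lift will occur.

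**The case against.** The strongest reply is that the plan never makes the last VAS the outcome. The ANOVA text names no occasions, and 18 readings are scheduled. The start-of-Visit-2 reading is free of any immediate induction, and the pre-rehearsal readings help too. All of this stands. A reader might infer that the trial has no means of telling carry-over from an immediate lift; the schedule does not support that. What is missing is narrower: a reading after the full intervention that is not taken right after a rehearsal.

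Second, the plan does not say that the gain in positive affect should last. It speaks of the end of the study. That also stands, so the plan cannot be charged with an unsupported claim of durability. Still, the study ends with a follow-up that lacks this measure. If only immediate affect is meant, the hypothesis should say so.

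Third, the Background argues that positive emotion during exposure may itself aid extinction learning. On that rationale in-session affect is of real interest, and reducing the post-rehearsal ratings to a manipulation check would be a debatable preference. This stands, and those ratings should be kept and reported.

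Fourth, a reader might infer that a group difference right after rehearsal is largely guaranteed by the instruction. The plan gives no effect of either rehearsal on the VAS, so the size of any such lift is unknown.

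Two replies carry less weight. The questionnaire lists use wording that need not be exhaustive, but no section schedules a VAS at follow-up. PVSS and BAS are collected at follow-up, but the analysis section assigns them to reward sensitivity.

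**Conclusion.** The point holds as a gap in measurement timing and in the definition of one outcome. Only one of the 18 scheduled VAS readings follows all eight rehearsals, and it directly follows the last of them. An end-of-study difference in positive affect could therefore be momentary mood only, and the start-of-Visit-2 and pre-rehearsal readings resolve this only in part.

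The size of the problem cannot be estimated from the plan. The 25%, 56% and 92% figures are t-test power at 37 per arm for assumed lifts of .3, .5 and .8 SD; they should not be read as error rates or bias. The conclusion rests on taking the questionnaire lists as written and on reading the end of the study as Visit 2 completion or later.

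This is a cheap improvement affecting one of several efficacy outcomes. The symptom and reward-sensitivity comparisons are not touched by it, and it does not put the trial as a whole in doubt.

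**What to change.** 1. Add the 1-9 VAS to the one-week follow-up survey.
2. In Statistics & Data Analysis, name the baseline, start-of-Visit-2 and follow-up readings as the occasions entering the repeated measures ANOVA, and call this the between-session positive-affect outcome.
3. Report the post-rehearsal readings separately as immediate, in-session affect. Keep them, but do not let them alone support the end-of-study claim.
4. If the follow-up rating cannot be added, for example because follow-up is already complete, limit the positive-affect claim to immediate affect and say so in the SAP before analysis.

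**Cost.** One short self-rating added to a survey of 5-10 minutes, and a few sentences of SAP text. The added rating is still a rating of the moment, made without supervision, so it will be noisier in setting than the visit ratings. It would nevertheless be the trial's only positive-affect reading after the full intervention that is not immediately preceded by a speech or a rehearsal.
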